12.2 Methods of statistical analyses

All analyses will be on the ITT unless otherwise specified. Baseline demographic and clinical data will be described between treatment and placebo study arms as mean ± standard deviation for continuous variables and compared using Student's T-test. Whereas discrete variables will be represented as a number and (%) and compared using the χ^2 or Fisher's exact test, as applicable.

The time course of continuous variables will be presented using standard descriptive summary statistics calculated at each scheduled measuring time point and the last individual measuring time point. Moreover, standard descriptive summary statistics will be calculated for the change (absolute or percent) from baseline to each scheduled measuring time point after baseline and the last individual measuring time point.

Due to the large number of study sites and the expected low number of patients per site it will not be appropriate to explore site effects.

Statistical significance will be defined using two-sided tests with α =0.05, unless otherwise specified. All statistical analyses will be performed by the **Statistical analyses** Department of Biostatistics using SAS version 9.4 (SAS Institute, Cary, North Carolina).

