12.2.1 Primary variable

There are two co-primary efficacy endpoints:

- 1. Difference in mean NTproBNP between the treatment and placebo study arms at 6 and 12 weeks.
- Proportion of patients that achieve a meaningful change from baseline in quality of life (≥ 5pts increase in KCCQ overall summary score) or NTproBNP (≥ 20% decrease) over 12 week treatment period between dapagliflozin 10 mg and placebo.

The first co-primary endpoint of this study is to compare dapagliflozin versus placebo on mean NTproBNP at 6 and 12 weeks. A generalized linear mixed model with a compound symmetry covariance structure to estimate the average effect over 6 and 12 weeks controlling for baseline NTproBNP. Gamma distribution and log link function will be used because of the skewness nature of NTproBNP. Center is included as a random factor to account for clustering of patients within centers.

The second co-primary endpoint, proportion of patients with $a \ge 5$ point KCCQ overall summary score increase or $a \ge 20\%$ decrease in NTproBNP at 6 or 12 weeks will be analyzed using Mantel-Haenszel test controlling for center.

Both co-primary endpoints will be analyzed in the entire patient cohort, and then within the subgroups of patients with and without diabetes (as pre-specified subgroup analyses).

Statistical significance will be determined using an ordered testing procedure; the alpha will be 0.05 for hypothesis 1. If hypothesis 1 is rejected then hypothesis 2 will be tested at α =0.05 level. However, if hypothesis 1 is not rejected hypothesis 2 will not be tested.

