12.3 Determination of sample size

For the first co-primary endpoint a sample size of 110 for each group will achieve 80% power with α =0.05 to detect a reduction in NTproBNP between the two groups of at least 302 pg/mL from baseline to 12 weeks. The assumptions for this calculation were derived from the BATTLESCARRED trial where the estimated standard deviation for NTproBNP was 1250 pg/mL. We expect the standard deviation in the DEFINE-HF Trial to be somewhat lower (961 pg/ml) given lower NTproBNP threshold. Of note, 302pg/mL reduction in NTproBNP is equivalent to 31.5% of the standard deviation in NTproBNP (based on the above assumption).

The second co-primary endpoint is a combined endpoint of $a \ge 5$ point KCCQ overall summary score increase or $a \ge 20\%$ decrease in NTproBNP. The sample size was determined using two independent groups where the anticipated control group percent change is 30%. A sample size of 110 for each group will achieve 80% power with α =0.05 to detect a difference in proportional change between the two groups of 18% from baseline to 12 weeks for the second co-primary endpoint.

There is an anticipated loss to follow-up of approximately 13% so the final sample size per group will be 125.

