1.3 Sample Size and Power

Planned Sample Size	• Approximately 110 patients will be enrolled in each arm.
Power Statement	• The first dual primary endpoint of this study is the average of 6- and 12- week NT pro-BNP. A generalized linear mixed model with patient as a random effect will be used to estimate the average effect over 6 and 12 weeks controlling for baseline NT pro-BNP and other pre-specified covariates. A gamma distribution with log link will be used to account for the skewed nature of NT pro-BNP. Several sensitivity analyses will be performed, one of which includes site as a random effect to account for clustering of patients within centers. For the first dual primary endpoint a sample size of 110 for each group will achieve 80% power with α =0.05 to detect a difference in NT pro-BNP between the two groups of at least 302 pg/mL from baseline to 12 weeks. The assumptions for this calculation were derived from the BATTLESCARRED trial where the estimated standard deviation for NT pro-BNP was 1250 pg/mL. We expect the standard deviation in the DEFINE-HF Trial to be somewhat lower (961 pg/ml) given lower NT pro-BNP threshold. Of note, 302pg/mL reduction in NT pro-BNP is equivalent to 31.5% of the standard deviation in NT pro-BNP (based on the above assumption). There is an anticipated non-completion rate of approximately 13% so the final sample size per group will be 125.
	 The second dual primary endpoint, the proportion of patients with a ≥ 5-point KCCQ overall summary score increase or a ≥ 20% decrease in NT pro-BNP, averaging over 6 and 12 weeks, will be analyzed using generalized linear mixed models controlling for baseline NT pro-BNP and KCCQ overall summary score as well as several additional covariates as specified below. A binomial distribution with logit link will be used. Several sensitivity analyses will be performed, one of which includes site as a random effect to account for clustering of patients within centers. Power was determined based on comparisons of proportions between two independent groups, where the anticipated control group percent change is 30%. A sample size of 110 for each group will achieve 80% power with α=0.05 to detect an absolute difference in proportions between the two groups of 18% from baseline to 12 weeks for the second dual primary endpoint.

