2.5 Multiple Testing

Both primary hypotheses will be tested at the 2-sided 5% significance level. In the case of non-significant findings for the first dual primary endpoint, the second dual primary endpoint will be tested at the 2-sided 5% significance level but will be regarded as an exploratory endpoint, and a nominal P value will be produced. No adjustments for multiplicity will be made for secondary and exploratory endpoints.

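### The 80% power stated for the second primary endpoint is a stand-alone figure; under the planned test order the chance of a formal claim is about 64–73% on the stated powers, and about 50–61% on the stated inputs for endpoint 1

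*Protocol*

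**What the plan says.** Protocol 12.3 gives a separate power for each primary endpoint at 110 per group.

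- **Endpoint 1 (NT-proBNP):** 80% power for a difference of 302 pg/mL with an SD of 961 pg/mL.
- **Endpoint 2 (responder composite):** with 30% responding on control, 80% power to "detect a difference in proportional change between the two groups of 18" percent. SAP 1.3 repeats both figures and makes clear that the 18 points are an absolute difference.

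On the error rate, protocol 12.2 says: "Statistical significance will be defined using two-sided tests with" alpha 0.05.

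On the order of testing, protocol 12.2.1 says: "Statistical significance will be determined using an ordered testing procedure; the alpha will be 0.05 for hypothesis 1". It goes on: "If hypothesis 1 is rejected then hypothesis 2 will be tested", again at 0.05. It closes the gate explicitly: "However, if hypothesis 1 is not rejected hypothesis 2 will not be tested". SAP 2.5 is softer in form, since endpoint 2 is still computed when endpoint 1 fails, but it then "will be regarded as an exploratory endpoint, and a nominal P value will be produced".

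On size, protocol 12.3 says: "There is an anticipated loss to follow-up of approximately 13% so the final sample size per group will be 125". The power statement in SAP 1.3 also arrives at 125 per group, but the planned-sample-size row of the same table reads: "Approximately 110 patients will be enrolled in each arm".

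**The concern.** Under a fixed sequence, a formal claim on endpoint 2 needs two rejections. Its probability is therefore the joint probability of rejecting both hypotheses, which cannot exceed the power of the first test. The sample-size sections never mention the order and give no joint figure, so a reader will take 80% as the chance that this named primary endpoint can be claimed if the assumed effects are real. A missed claim would then look like evidence against the effect when the design makes it a fairly common outcome.

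The gate also carries any weakness of endpoint 1 into endpoint 2. If the first test has less power than stated, the second inherits the shortfall.

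**Working it through.** **Inputs.** From protocol 12.3: n = 110 per group; difference 302 and SD 961 pg/mL; responder rates 30% and 48%. From protocol 12.2: two-sided alpha 0.05. From protocol 12.2.1 and SAP 2.5: endpoint 2 is claimable only after endpoint 1. The correlation rho between the two test statistics is not in the documents and is an assumption here.

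**1. Endpoint 2 alone (reproducing the plan's figure).** Pooled two-proportion test, mean rate 0.39:
- SE under the null = √(2 × 0.39 × 0.61 / 110) = 0.06577
- SE under the alternative = √((0.30 × 0.70 + 0.48 × 0.52) / 110) = 0.06464
- Power = Φ((0.18 − 1.960 × 0.06577) / 0.06464) = Φ(0.790) = 78.5%

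The unpooled version gives 79.5%. The stated 80% is reproduced to within about two points.

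**2. Endpoint 1 alone.** Two-sample comparison of means:
- SE = 961 × √(2/110) = 129.6
- Power = Φ(302/129.6 − 1.960) = Φ(0.371) = 64.5% (noncentral t: 64.1%)

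The stated 80% is not reproduced. On these inputs, 80% needs 2 × (1.960 + 0.842)² × (961/302)² ≈ 159 per group. Using all 125 randomised gives only 70.0% two-sided. At 110 per group, 80% would need a residual SD of about 799. Since 961 × √(1 − r²) = 799 at r ≈ 0.555, this corresponds to a baseline correlation of about 0.55–0.56 under covariance adjustment. Neither document states such a value.

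**3. Probability of a formal claim on endpoint 2.** P(both reject) = Φ₂(Φ⁻¹(p₁), Φ⁻¹(p₂); rho), where Φ₂ is the bivariate normal distribution function. At rho = 0 this is p₁ × p₂.

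| Powers used (p₁, p₂) | rho 0 | rho 0.4 | rho 0.8 | rho 1 (ceiling) |
|---|---|---|---|---|
| Both as stated (80%, 80%) | 64.0% | 67.6% | 72.9% | 80% |
| Recomputed (64.5%, 78.5%) | 50.6% | 55.3% | 61.2% | 64.5% |

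With the noncentral t value of 64.1% for endpoint 1, the second row starts at 50.3%, 55.0% and 60.9%.

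**4. Range of rho.** A positive correlation is expected because endpoint 2 counts a fall of at least 20% in NT-proBNP. A simple simulation fixed the control responder rate at 30%, let 5% to 30% of patients respond on NT-proBNP, and took KCCQ response as independent. It gave correlations of about 0.16 to 0.76, within the range shown.

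**5. Separating the two causes.** The test order alone takes 80% to 64–73%. The further fall to 50–61% comes almost entirely from the endpoint 1 power being 64% rather than 80%. Using 78.5% instead of 80% for endpoint 2 accounts for only about one point.

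**The case against.** The strongest reply is that the endpoint 2 figure is not an arithmetic error. It is the power of one comparison, it reproduces, and neither document claims anything about both tests succeeding. That stands: the fault is a missing figure for the procedure actually planned.

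A second reply is that the planned analyses are stronger than the simple two-group calculations used here. Endpoint 1 is to be analysed with a baseline-adjusted gamma mixed model over weeks 6 and 12, and the SAP analyses endpoint 2 by covariate-adjusted logistic regression. This also stands in part. For illustration only, a baseline correlation of 0.5 to 0.7 would raise endpoint 1 power to about 77–90% and the joint probability to about 60–77% for rho 0 to 0.8. But the power statements claim no such gain and give no input for one, so it cannot support the 80% as written.

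Some stronger readings are tempting but not supported:
- **The test order alone brings the figure to 50–61%.** It does not; step 5 of the working separates the two causes.
- **The 50–61% range follows from the plan's inputs alone.** It also needs an assumed correlation. Only the ceiling of about 64% is free of that assumption.
- **The trial will have only about 96 evaluable per arm** (110 × 0.87 = 95.7). The SAP row read by itself implies this, but the same SAP section and protocol 12.3 say 125 per group, and the protocol synopsis says about 250 in total. The row is a wording slip.
- **125 × 0.87 = 108.75 contradicts 110.** With a loss given only as approximately 13%, this is rounding.

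**Conclusion.** The point holds with two distinct parts. First, the 80% for endpoint 2 is acceptable only as stand-alone power. It is not the chance of a formal claim, which is about 64–73% even if both stated powers are right. Second, the stated inputs for endpoint 1 deliver about 64% rather than 80%, which lowers that chance to about 50–61% and caps it at about 64%.

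These figures rest on unadjusted two-group calculations, approximate bivariate normality of the test statistics, and an assumed correlation of 0 to 0.8. The direction does not depend on the correlation: with both powers at 80%, the joint probability reaches 80% only if the two statistics are perfectly correlated, and endpoint 2 also counts patients who respond on KCCQ alone.

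The error rate is not affected. The protocol and SAP differ on whether endpoint 2 is computed after a failed endpoint 1, but they agree that no formal claim follows.

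**What to change.** In protocol 12.3 and SAP 1.3:

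1. Restate endpoint 1 power as about 64% on the unadjusted two-group inputs. Alternatively, state and justify the variance reduction from baseline adjustment that supports 80% (for example, a baseline correlation of about 0.55–0.56).
2. Label the endpoint 2 figure as stand-alone power, about 78%.
3. Add the probability of a formal endpoint 2 claim under the planned order, with its assumed correlation range: about 50–61% on the unadjusted inputs, or about 64–73% if both 80% figures are justified.

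Items 1 and 3 must be changed together. Quoting 50–61% beside an unchanged 80% for endpoint 1 would make the section inconsistent.

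In SAP 1.3, change the planned-sample-size row to 125 randomised per arm (about 110 evaluable), to agree with the rest of that section and with the protocol.

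The cost is less favourable published figures and, if 80% is to be defended for endpoint 1, a source for the baseline correlation. The tests, the alpha and the number of patients do not change.

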13.2 Overdose

Overdose is defined as the accidental or intentional ingestion of any dose of investigational product that is considered both excessive and medically important. Dapagliflozin has been well tolerated at doses of up to 500 mg/day in single dose testing in healthy volunteers and up to 100 mg/day in repeat dose testing for 14 days in healthy volunteers and patients with type 2 diabetes. If an overdose is suspected, monitoring of vital functions as well as treatment, as appropriate, should be performed. If an overdose occurrence meets the criteria for a Serious Adverse Event, then it must be reported as Serious Adverse Event.

13.3 Pregnancy

Any pregnancy during the course of this study should be recorded. Pregnancy itself is not regarded as an Adverse Event unless there is a suspicion that the investigational product under study may have interfered with the effectiveness of a contraceptive medication.

If any pregnancy occurs in the course of the study, the patient should be discontinued, the investigational product should be stopped and then investigators or other site personnel must inform appropriate **sector** representatives immediately but no later than the end of the next business day of when he or she becomes aware of it.

14 BIOMARKER SUBSTUDY

A biomarker substudy will be conducted. Specimens will be collected for exploratory biomarker testing from all patients at the Randomization, Week 6 and Week 12 visits to assess the impact of dapagliflozin versus placebo on known markers of myocardial fibrosis/necrosis, inflammation, and oxidative stress. Detailed collection, processing, storage and shipment instructions are provided in the central laboratory manual. Information regarding the biomarker substudy is included in appendix C.

15 FUTURE RESEARCH

The residual sample from the biomarker substudy will be stored indefinitely to allow for possible future research. Information regarding the storage and possible use of banked biospecimens is included in appendix C.

16 ARRYTHMIA SUBSTUDY

An arrhythmia substudy will be conducted. Patient participation will be optional. At the screening visit, those likely to be enrolled will be given the option to participate in the arrhythmia substudy. If they elect to enroll they will wear a holter monitor for 14 days to establish a baseline. The 14-day holter will be

repeated at the 6-week visit to compare change in arrhythmia burden. Information regarding the arrhythmia substudy is included in appendix D.

17 SensiVest Lung Fluid Volume Measurements

SensiVest utilizes remote dielectric sensing ReDS[™] technology, to estimate lung fluid volumes. The technology has been adapted from the military who used it to see inside buildings and to find survivors among rubble. Sensible Medical has adapted the same principles and created a vest that when worn sends low-power electromagnetic energy through the lungs, which decipher air content from fluid¹⁹. Two sensors are attached to the body: one anteriorly on the chest and the other on the back of the patient. Each sensor both transmits and receives the energy either reflected from or transferred through the pulmonary tissue. The signal received reflects the dielectric properties of the section of the lung between the sensors. Water has a very high dielectric coefficient while air in contrast has the lowest dielectric coefficient. These physical properties make pulmonary tissue ideal to sensitively quantify the ratio of fluid to air (or in the case of heart failure estimate volume status and pulmonary edema).² The device has received both FDA 510k clearance and European CE markings for non-invasive lung fluid monitoring. The waves emitted are low frequency, which do not interfere with any other implantable devices¹⁷. The accuracy of ReDS was first established using CT as a gold standard and correlating changes in ReDS values among porcine models of heart failure undergoing both fluid challenge and then diuresis. As a part of the study, patients at selected sites will have blinded lung/fluid volume measurements at rest during the randomization (week 0), 6, 12 and 13 week visits. Site personnel will remain blinded to the Sensivest measurement results; de-identified and blinded Sensivest measurements will be accessible to the National Coordinating Center staff. (See appendix E for further details).

19 APPENDIX A: HEART FAILURE HOSPITALIZATION/URGENT OUTPATIENT VISIT

A **Heart Failure Event** includes hospitalization for heart failure and may include urgent outpatient visits. Heart failure hospitalizations should remain delineated from urgent visits.

A Heart Failure Hospitalization is defined as an event that meets ALL of the following criteria:

- The patient is admitted to the hospital with a primary diagnosis of heart failure
- The patient's length-of-stay in hospital extends for at least 24 hours (or a change in calendar date if the hospital admission and discharge times are unavailable)
- The patient exhibits documented new or worsening symptoms due to heart failure on presentation, including at least ONE of the following:
 - Dyspnea (dyspnea with exertion, dyspnea at rest, orthopnea, paroxysmal nocturnal dyspnea)
 - Decreased exercise tolerance
 - Fatigue
 - o Other symptoms of worsened end-organ perfusion or volume overload
- The patient has objective evidence of new or worsening heart failure, consisting of at least TWO physical examination findings OR one physical examination finding and at least ONE laboratory criterion), including:
 - Physical examination findings considered to be due to heart failure, including new or worsened:
 - Peripheral edema
 - Increasing abdominal distention or ascites (in the absence of primary hepatic disease)
 - Pulmonary rales/crackles/crepitations
 - Increased jugular venous pressure and/or hepatojugular reflux
 - S3 gallop
 - Clinically significant or rapid weight gain thought to be related to fluid retention
 - Laboratory evidence of new or worsening heart failure, if obtained within 24 hours of presentation, including:
 - Increased B-type natriuretic peptide (BNP)/ N-terminal pro-BNP (NT- proBNP) concentrations consistent with decompensation of heart failure (such as BNP > 500 pg/mL or NT-proBNP > 2,000 pg/mL). In patients with chronically elevated natriuretic peptides, a significant increase should be noted above baseline.
 - Radiological evidence of pulmonary congestion
 - Non-invasive or invasive diagnostic evidence of clinically significant elevated left- or right-sided ventricular filling pressure or low cardiac output. For example, echocardiographic criteria could include: E/e' > 15 or D-dominant pulmonary venous inflow pattern, plethoric inferior vena cava with minimal collapse on inspiration

OR

 Invasive diagnostic evidence with right heart catheterization showing a pulmonary capillary wedge pressure (pulmonary artery occlusion pressure) • \geq 18 mmHg, central venous pressure \geq 12 mmHg, or a cardiac index < 2.2 L/min/m²

- The patient receives initiation or intensification of treatment specifically for heart failure, including at least ONE of the following:
 - Augmentation in oral diuretic therapy
 - Intravenous diuretic, inotrope, or vasodilator therapy
 - Mechanical or surgical intervention, including:
 - Mechanical circulatory support (e.g., intra-aortic balloon pump, ventricular assist device)
 - Mechanical fluid removal (e.g., ultrafiltration, hemofiltration, dialysis) Using available information, Heart Failure will be categorized based on the following:
 - Left ventricular ejection fraction (LVEF)
 - Type
 - Etiology
- An **Urgent Heart Failure Visit** is defined as an event that meets all of the following:
 - The patient has an urgent, unscheduled office/practice or emergency department visit for a primary diagnosis of heart failure, but not meeting the criteria for a heart failure hospitalization.
 - All signs and symptoms for heart failure hospitalization (i.e., 3) symptoms; 4) physical examination findings/laboratory evidence of new or worsening heart failure, as indicated above) must be met
 - The patient receives initiation or intensification of treatment specifically for heart failure, as detailed in the above section.

20 APPENDIX B: KANSAS CITY CARDIOMYOPATHY QUESTIONNAIRE (KCCQ)

Kansas City Cardiomyopathy Questionnaire (KCCQ)

The following questions refer to your **heart failure** and how it may affect your life. Please read and complete the following questions. There are no right or wrong answers. Please mark the answer that best applies to you.

1. **Heart failure** affects different people in different ways. Some feel shortness of breath while others feel fatigue. Please indicate how much you are limited by **heart failure** (shortness of breath or fatigue) in your ability to do the following activities over the past 2 weeks.

Activity	Extremely Limited	Quite a bit Limited	Moderately Limited	Slightly Limited	Not at all Limited	Limited for other reasons or did not do the activity
Dressing yourself						
Showering/Bathing						
Walking 1 block on level ground						
Doing yardwork, housework or carrying groceries						
Climbing a flight of stairs without stopping						
Hurrying or jogging (as if to catch a bus)						

2. Compared with 2 weeks ago, have your symptoms of **heart failure** (shortness of breath, fatigue, or ankle swelling) changed?

My symptoms of **heart failure** have become... Much worse Slightly Not changed Slightly better Much better I've had no symptoms worse Ore the last 2 weeks 3. Over the past 2 weeks, how many times did you have **swelling** in your feet, ankles or legs when you woke up in the morning?

Every n	norning	3 or more times a week, but not every day	1-2 times a week	Less than wee	once a Never o k past 2	over the weeks
C]				I C]
4. Over t It	he past 2 v has been .	weeks, how much ł 	nas swelling in you	ır feet, ankle	es or legs bothered	you?
Extre	emely	Quite a bit	Moderately	Slightly	Not at all	I've had no
bothe:	rsome	bothersome	bothersome	bothersom	e bothersome	swelling
5. Over t what y	he past 2 v ou want	weeks , on average, ??	how many times h	nas fatigue li	imited your ability	to do
All of the time	Several tir per dav	mes At least once y a day	3 or more times per week but not every day	1-2 times per week	Less than once a week	Never over the past 2 weeks
1. Over It has b Extrem botherso	the past 2 been ely ome	weeks, how much Quite a bit bothersome	has your fatigue b Moderately bothersome b	oothered you Slightly oothersome	? Not at all bothersome	I've had no fatigue
7. Over the ability	he past 2 v to do wha	veeks , on average, It you wanted?	how many times h	nas shortnes	s of breath limited	d your
All of the time	Several tin per dav	mes At least once y a day	3 or more times per week but not every day	1-2 times per week	Less than once a week	Never over the past 2 weeks

8. Over the past 2 weeks, how much has your **shortness of breath** bothered you?

It has been ...

Extremely bothersome	Quite a bit bothersome	Moderately bothersome	Slightly bothersome	Not at all bothersome	I've had no shortness of breath
9. Over the past 2 in a chair or with a	weeks, on averag t least 3 pillows t	ge, how many t to prop you up	imes have you because of sho	been forced to ortness of breat	sleep sitting up th?
Every night	3 or more time week, but not eve	es a 1-2 ery day v	times a Le veek □	a week	Never over the past 2 weeks
10. Heart failure sy to do, or whom	mptoms can worse to call, if your hea	en for a number rt failure gets wo	of reasons. How orse?	w sure are you th	nat you know what
Not at all sure	Not very sure	Somewha	t sure Mc	ostly sure	Completely sure
11. How well do you from getting woDo not understandat all	u understand what rse? (for example, d Do not under very we	t things you are a weighing yourse rstand Son II und	able to do to ke elf, eating a low newhat erstand	ep your heart fai salt diet etc.) Mostly understand	i lure symptoms Completely understand
12. Over the past 2	weeks , how much	has your heart f	ailure limited y	our enjoyment o	f life?
It has extremely limited my enjoyment of life	It has limited m enjoyment of lif quite a bit	y It has mod e limited enjoyment	erately It h my lir : of life enjoy	as slightly I mited my r yment of life	t has not limited ny enjoyment of life at all
			l		

13. If you had to spend the rest of your life with your **heart failure** the way it is right now, how would you feel about this?

Not at all	Mostly	Somewhat	Mostly	Completely
satisfied	dissatisfied	satisfied	satisfied	satisfied

14. Over the past 2 weeks, how often have you felt discouraged or down in the dumps because of your **heart failure**?

l felt that way	I felt that way	l occasionally	l rarely felt that	l never felt that
all of the time	most of the time	felt that way	way	way

15. How much does your **heart failure** affect your lifestyle? Please indicate how your **heart failure** may have limited your participation in the following activities over the past 2 weeks.

Please place an X in one box on each line

Activity	Severely limited	Limited quite a bit	Moderately limited	Slightly limited	Did not limit at all	Does not apply or did not do for other reasons
Hobbies, recreational activities						
Working or doing household chores						
Visiting family or friends out of your home						
Intimate relationships with loved ones						

Place an X in one box on each line

